#### Embryo-foetal studies

Embryo-foetal studies were done in the rat and rabbit, using doses of 100, 300, and 1000 mg/kg/day. YF476 had no effect on embryo-foetal survival, growth or development.

#### Metabolism

The metabolism of parent C-YF476 was most efficiently catalysed by human > dog > rat *in vitro*. Phase I and II metabolites were formed. There was no evidence for formation of unique major human metabolites, although the main metabolite was different from that formed by rat and dog. Thus, the rat and dog are appropriate species to assess the potential toxicity of YF476 in humans.

Further details of non-clinical studies of YF476 are in the Investigator's Brochure.

#### 7.8.5 Completed studies in healthy subjects

HMR has completed and reported 9 studies of Y	YF476 in 162 healthy men and women.
---	-------------------------------------

Study code	Design	n	YF476 dose (mg)	Comparator
96-001	single, dose-rising, double-blind, incomplete crossover	15 (M)	0.5-100	placebo
96-016	single-dose, double-blind, 5-way crossover	21 (M/F)	5, 25, 100	placebo & ranitidine 150 mg
96-018	7-day dosing, double-blind, 4 parallel groups	49 (M/F)	25 & 100 bd	omeprazole 20 mg od
97-010	14-day dosing, double-blind, 4 parallel groups	49 (M)	5, 10 & 25 od	placebo
01-022	single-dose, double-blind, 5-way crossover	12 (M/F)	1, 5, 25 & 100	placebo
01-023	7-day dosing, open	10 (M/F)	100 bd	placebo Days 0 & 14
T-001 (05-021)	YF476 & rabeprazole, alone & in combination, 6-weeks' dosing, double-blind, 3 parallel groups	32 (M/F)	100 od	rabeprazole
T-009 (07-013)	single-dose, open, fed-fasted comparison	12 (M/F)	100	_
T-011 (07-024)	new formulation, single, dose-rising, double-blind, fed-fast comparison	10 (M/F)	50–400	placebo

In all studies, YF476 was well tolerated. Adverse events were minor and transient; they resolved spontaneously, and occurred in subjects given placebo as well as those given YF476. There were no effects on vital signs, ECG, or safety tests of blood and urine, and no clinically significant adverse events.

Single doses of YF476 caused dose-dependent increases in 24-h gastric pH. The effect of a single dose of YF476 lasted much longer than that of ranitidine, (an  $H_2$  receptor antagonist). However, the effect of YF476 on 24-h gastric pH was mostly lost after repeated doses, whereas that of omeprazole persisted.

Single doses of YF476 also caused dose-dependent inhibition of pentagastrin-induced falls in gastric pH and increases in gastric volume and  $H^+$  output. Again, the effect on gastric pH was mostly lost after repeated doses of YF476. But, the effects on gastric volume and  $H^+$  output persisted. So, gastrin receptors must be blocked after repeated doses of YF476. YF476 also caused dose-dependent increases in blood gastrin, which persisted after repeated doses, further evidence that gastrin receptors are blocked after repeated doses of YF476.

We do not know the mechanism for the reduced effect of YF476 on gastric pH after repeated doses of YF476, but an effect on buffering of gastric juices seems a possibility. We are doing further studies to assess the mechanism.

There was no evidence of an effect of YF476 on QT interval. However, until we have more experience of YF476, patients with prolonged QT interval should be excluded from clinical trials of YF476 (Shah 2002).

YF476 was measured by the method of Redrup *et al* (2002). In early studies (before 2001), YF476 had linear pharmacokinetics, and consistent bioavailability. Absorption was rapid, and the terminal elimination half-life was about 6 h. AUC0-24 after 100 mg, the largest dose studied, was about 650 ng.h/mL, which is about a 5 to 60-fold safety margin in terms of AUC0-24 at NOAEL in the 13-week toxicology studies. Steady state was reached by Day 3, and there was no accumulation by Day 7. Only 1–2% was excreted unchanged in the urine.

However, in two subsequent studies (T-001 and T-009), for which we used a different formulation, plasma concentrations of YF476 were only about 10–15% of those achieved in the early studies. Despite the low bioavailability, YF476 showed good pharmacodynamic effects in study T-001 (effects of rabeprazole 40 mg and YF476 100 mg, alone and in combination for 6 weeks, on gastric function). In that study, gastric function was assessed by: 24-h ambulatory gastric pH; pentagastrin-stimulated gastric pH, volume and H+ output; 24-h serum gastrin profile; and 24-h plasma CgA profile (CgA is a biomarker for ECL-cell activity).

On Day 1 or 2, YF476 and rabeprazole by themselves gave similar results. They both:

- inhibited pentagastrin-induced increase in volume of gastric aspirate and H+ secretion;
- increased 24-h ambulatory gastric pH; and
- increased serum gastrin (a biomarker for gastric acid production), but did not affect plasma CgA (a biomarker for ECL-cell activity).

At 6 weeks, YF476:

- was as effective as rabeprazole in reducing gastric acid volume and H+ secretion;
- was as effective as rabeprazole in increasing serum gastrin, a biomarker for gastric acid production;
- did not increase plasma CgA, whereas rabeprazole increased it substantially;
- abolished the rabeprazole -induced increase in CgA; and
- augmented gastric acid suppression by rabeprazole without affecting the increase in gastric pH by rabeprazole.

The combination was more effective than either rabeprazole or YF476 alone in suppressing gastric acid production. Furthermore, the combination did not lose its effect on gastric pH after 6 weeks' dosing. On the contrary, the effect increased.

That YF476 completely suppressed the rabeprazole -induced increase in plasma CgA suggests that YF476 prevented rabeprazole -induced hypergastrinaemia from stimulating the ECL cells. Overall, the effects of YF476 are consistent with antagonism of gastrin receptors.

We conclude that YF476 augments PPI-induced gastric acid suppression and prevents increased ECL-cell activity caused by PPI-induced hypergastrinaemia. Also, whatever the cause of the loss of effect of YF476 on gastric pH after repeated dosing, it is unlikely to impair the ability of YF476 to prevent the unwanted effects of a PPI.

We now have a new formulation of YF476, which was made by spray-drying a solution of YF476 with hydroxypropylmethylcellulose (HPMC). That process generated amorphous YF476 stabilised by an HPMC polymer matrix. We tested single doses (range 50–400 mg) in study T-011. Plasma concentrations were similar to those in the early studies of YF476. After 100 mg of the new formulation, mean  $C_{max}$  was 265.3 ng/mL and mean AUC0-24 was 527 ng.h/mL. After 400 mg, mean  $C_{max}$  was 704.3 ng/mL and mean AUC0-24 was 1557 ng.h/mL. The new formulation will be used in this study.

For further information on the non-clinical and clinical studies of YF476, refer to the Investigator's Brochure.

#### 7.8.6 Studies in progress in healthy subjects

Study T-012 (05-029): The aim is to assess the absolute bioavailability of the latest formulation of YF476. 6 subjects received a single oral 100mg dose of YF476 close together with a single intravenous 15  $\mu$ g dose of C–YF476. Blood samples are being assayed for 'cold' YF476 and C–YF476. Preliminary results show that the absolute bioavailability of YF476 is about 15%.

Study T-013 (09-013): This study aims to assess the effect of different 14-day dose regimens of YF476 on the increase in circulating CgA induced by a PPI (esomeprazole 40 mg daily for 4 weeks).

To date, 24 subjects have completed the study. Preliminary results show that 25 mg YF476 daily completely suppressed the increase in CgA induced by esomeprazole. YF476 was well tolerated.

#### 7.9 Rationale for this study, and choice of study design

It is clear from the aforementioned information that there are compelling reasons for treating patients with type I or type II gastric carcinoids – both of which are gastrin dependent – with YF476, a gastrin receptor antagonist. Indeed, the European Commission and the USA Food and Drug Administration have designated YF476 an

Orphan Medicinal Product for treatment of patients with gastric carcinoids (European Commission 2007, Food and Drug Administration 2009).

We need to ask ourselves several questions about the trial design.

#### *First, what type of patient should we study?*

In this first trial of YF476 in patients with gastric carcinoids, we will study only type I patients for the following reasons. First, the characteristics of patients with type I gastric carcinoids are very different from those of patients with type II gastric carcinoids. Therefore, types I and II gastric carcinoids merit separate trials to assess the efficacy of YF476. Second, there is already some evidence from one patient with type I gastric carcinoids that YF476 will be effective; large multiple gastric carcinoids in a patient with chronic atrophic gastritis, pernicious anaemia and hypergastrinaemia regressed after 4-weeks' intravenous infusion of JB95008, a gastrin receptor antagonist with poor oral bioavailability (Chau et al 2006). Several years later, the tumours have not regrown ([name], personal communication). Third, although gastric carcinoids are rare tumours, type I are more common and should be less difficult to find. Fourth, the existing treatment of type II patients is likely to be more complicated than that of type I patients. Type II patients will almost certainly be receiving several treatments, such as high-dose PPI and perhaps other therapy to suppress gastric acid secretion - for treatment of peptic ulcer disease - whereas type I patients are likely to be receiving injections of vitamin B12 only – for treatment of pernicious anaemia. Finally, a common protocol for types I and II would be more complicated and not ideal for a first trial of YF476.

#### Second, what should be the dose regimen of YF476?

Patients with type I gastric carcinoids have raised serum CgA (Borch *et al* 1997; Peracchi et al 2005), which is reduced by treatment with octreotide, a somatostatin analogue (Fykse et al 2004 and 2005; Campana et al 2008; Pregun et al 2009). Thus, serum CgA seems to be a useful biomarker for assessing the dose regimen of YF476 for the proposed study. In that respect, we have shown that concomitant administration of 100 mg YF476 daily completely suppressed the huge increase in plasma CgA induced by rabeprazole 20 mg daily for 6 weeks in healthy subjects. We now know that the formulation of YF476 used in that study was poorly bioavailable -100 mg is equivalent to about 15 mg of the current formulation, so that might be a suitable dose of YF476 for the proposed study. However, patients with chronic atrophic gastritis (CAG) have hypergastrinaemia for many years before they develop gastric carcinoids, so a larger dose of YF476 seems justified. Also, patients with CAG are precious and we don't want to underdose them. Therefore, we plan to treat patients with 50 mg once daily for up to 12 weeks, and allow the principal investigator to increase the dose after 6 weeks to 75 or 100 mg daily, if necessary. Similar or higher doses of YF476 have been well tolerated in all the completed studies in healthy subjects, so safety should not be rate limiting. Toxicology and toxicokinetic studies support dosing of YF476 for up to 13 weeks. If the response of the one patient with

type 1 gastric carcinoids who was treated with JB95008 ('Gastrazole') is typical, treatment with YF476 for less than 12 weeks might be enough.

Food increases the bioavailability of YF476 in healthy subjects, so patients will take YF476 with breakfast.

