#### Toxicology studies

In acute toxicity studies in dogs, 100 and 500 mg/kg/day resulted in similar plasma concentrations of YF476, and caused no adverse effects. Therefore, 100 mg/kg/day was the highest dose tested in a 13-week toxicity study. Changes in pancreas weight and histopathology were observed in some animals, and serum amylase was elevated in one low-dose male. However, there was no clear relationship to dose, and no relationship between histological changes and individual organ weights. So, those changes were considered to be incidental findings, and unlikely to be related to

treatment with YF476. Therefore, 100 mg/kg/day was taken to be the nominal noobservable-adverse-effect level (NOAEL) in dogs.

In a 13-week toxicity study in rats, the NOAEL was 100 mg/kg/day. At 300 and 1000 mg/kg/day, some animals had minor, reversible changes in enzyme activities and heart weight, and discoloured urine and pale faeces. Minor histopathological lesions in the heart and pancreas of 4 treated animals and 1 control animal were observed. Those lesions are part of the background pathology commonly seen in laboratory rodents, so were considered to be spontaneous lesions unrelated to treatment with YF476.

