#### **Extended treatment**

Some patients will be eligible for extended treatment with YF476, as described below. To be eligible for further treatment, the patient must have benefitted from 12 weeks' treatment, and have tolerated YF476 well, and must give fully informed written consent.

**Visit 8** will be to inform the patient about the extended dosing period and prescribe YF476 capsules. If the investigator thinks that a new baseline gastroscopy and blood sampling (for safety, gastrin and CgA) is necessary, this will be carried out.

**Visit 9** will be 12 weeks after starting extended treatment with YF476, to assess tolerability, safety and blood levels of gastrin, CgA and YF476.

**Visit 10** will be 24 weeks after starting extended treatment with YF476, to assess tolerability and safety, to repeat the gastroscopy and gastric biopsies, and to take blood samples to assess blood levels of gastrin, CgA and YF476.

**Visit 11** will be 36 weeks after starting extended treatment with YF476, to assess tolerability, safety and blood levels of gastrin, CgA and YF476.

**Visit 12** will be 52 weeks after starting extended treatment with YF476, to assess tolerability and safety, to repeat the gastroscopy and gastric biopsies, and to take blood samples to assess levels of gastrin, CgA and YF476.

A formal follow-up visit will be omitted, as the patients are closely followed by the investigator as part of their standard healthcare.

The end of the trial will be the last visit by the last subject.

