# 20 Trial documentation

# 20.1 Protocol amendments

After the protocol has been approved by the main REC and the MHRA, no changes may be made without the agreement of both the investigator and the sponsor.

The MHRA and main REC do not need to approve any substantial change to the protocol that needs to be implemented urgently to avoid an immediate hazard to trial subjects. The sponsor will ensure that the MHRA and main REC are informed of urgent amendments in accordance with the detailed guidance to EU Directive 2001/20/EC and the standard operating procedures issued by NRES for NHS RECs.

All agreed protocol amendments will be recorded on a written agreement which will be signed and dated by the investigator and sponsor, and attached to the original protocol. The REC and/or MHRA must approve substantial amendments before they are implemented.

The following changes to the trial plan are permitted by this protocol, and will not be considered as amendments.

- (a) Additional visits, for example to monitor blood pressure, will be arranged if there is a potential risk of a drug-drug interaction (see Appendix 1).
- (b) Additional blood or urine samples may be taken for safety tests if required. The total volume of additional blood taken will not exceed 100 mL. Laboratory safety tests will be repeated, if the investigator has any safety concerns.
- (c) Up to 3 additional visits to the clinic will be permitted, in the event of a technical failure and/or it extra safety tests are needed.
- (d) Additional laboratory tests for ECL-cell markers, biomarkers and/or histology will be done on the gastric biopsies, if the results of other tests suggest that additional tests would be worthwhile.
- (e) Stored serum will be used for laboratory tests not yet defined but related to this trial only.
- (f) Visits 3 and 5 may be made up to 2 days before or after the scheduled day. Visits 4, 6 and 7 may be made up to 3 days before or after the scheduled day. Visits 9-12 may be up to 5 days before or after the scheduled day. Patients will be given sufficient YF476 to cover any delays. Therefore, up to 33 days extra YF476 may be taken by each patient, although every effort will be made to arrange patient's visits on the scheduled days.
- (g) It might not be possible to take a video of every gastroscopy. Photographs should suffice.

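### Section 7.9 states toxicology support for up to 13 weeks of dosing, the extension allows up to 52 weeks, and nothing in the protocol reconciles the two

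*Protocol*

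**What the plan says.** **Stated support.** The dose-regimen part of Section 7.9 plans an initial course of at most 12 weeks and adds: "Toxicology and toxicokinetic studies support dosing of YF476 for up to 13 weeks".

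**Where the 13 weeks comes from.** In Section 7.8.4, for dogs: "Therefore, 100 mg/kg/day was the highest dose tested in a 13-week toxicity study". For rats: "In a 13-week toxicity study in rats, the NOAEL was 100 mg/kg/day". Section 7.8.5 gives "about a 5 to 60-fold safety margin in terms of AUC", measured "at NOAEL in the 13-week toxicology studies".

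**Permitted dosing.** Sections 2.6 and 9 add an extension for patients who benefitted from the first 12 weeks, tolerated the drug well and consent. Its last visit, Visit 12, "will be 52 weeks after starting extended treatment with YF476". Section 11.1 carries over each patient's last daily dose and leaves open 75 or 100 mg, or a reduction to 25 mg. Under Section 14.10, complete regression at Visit 10 (24 weeks) ends dosing; otherwise it continues.

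**Risk text.** The endoscopy item in Section 7.9 puts the number of gastroscopies at a maximum of four. The closing part of that section concludes that benefit greatly outweighs risk and does not mention the extension.

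**The concern.** The protocol sets itself a duration for which it claims non-clinical support, then schedules dosing well past it. The 13 weeks is not a stray figure: it is the length of both repeat-dose studies with a stated length, and the human safety margin is expressed against those studies. An AUC margin compares daily exposures at the no-effect level, so it does not by itself speak to longer dosing.

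At stake is whether the stated safety basis matches the exposure the protocol authorises. Someone judging the extension from this document finds a rationale written around 12 weeks and a benefit-risk conclusion whose listed risks do not include a year of further dosing.

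**Working it through.** **Inputs**
- Duration stated as supported: 13 weeks (Section 7.9).
- Repeat-dose toxicity studies with a stated length: 13 weeks in dogs, 13 weeks in rats (Section 7.8.4).
- Initial course: up to 12 weeks (Section 11.1).
- Extension: up to 52 weeks (Sections 2.6, 9, 14.12), or 24 weeks if stopped at Visit 10 (Section 14.10).

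**Step 1: reproduce the stated figure.** The 13 weeks in Section 7.9 equals the length of both studies in Section 7.8.4. It also covers the initial course as scheduled: 12 weeks is less than 13.

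**Step 2: compare with the extension.**
- Full extension: 52/13 = 4.0 times the stated duration. Share covered: 13/52 = 25%. Weeks beyond: 52 − 13 = 39.
- Stop at Visit 10: 24/13 = 1.8 times. Share covered: 13/24 = 54%. Weeks beyond: 24 − 13 = 11.

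The extension as scheduled exceeds 13 weeks on either route, without counting the initial course.

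**Step 3: look for support elsewhere in the protocol.**
- Section 7.8.4 lists the other non-clinical studies without giving any longer repeat-dose duration.
- The longest human dosing described is 6 weeks, in healthy subjects (study T-001, Section 7.8.5). Its formulation gave only about 10–15% of the plasma concentrations in the early studies, and Section 7.9 equates its 100 mg to about 15 mg of the current product. The other repeat-dose studies in Sections 7.8.5 and 7.8.6 gave YF476 for 7 or 14 days.
- Sections 2.6, 9, 11.1 and 14.8 to 14.12 describe the extension but give no rationale for its length.

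**Step 4: check what the risk text covers.** The initial trial has gastroscopies at Visits 2, 4, 6 and 7, which is 4 and matches Section 7.9. The extension adds Visits 10 and 12, and Visit 8 if the investigator wants a new baseline: 4 + 2 = 6, or 4 + 3 = 7. The endoscopy item therefore counts the initial trial only.

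**The case against.** **The 13-week sentence was about the initial regimen.** It sits in a paragraph justifying the 12-week course and does not mention the extension. That is a fair reading, but it does not close the gap. If the sentence is a general limit, the extension exceeds it; if it concerns the initial course only, the extension has no stated support.

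**Longer data may exist.** Sections 7.8.4 and 7.8.5 refer to the Investigator's Brochure for more detail, and the Brochure is not at hand. A reader might infer that longer toxicology is lacking, or that the extension is unsafe. The protocol shows neither. This objection stands, and it limits the point to what the protocol itself says.

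**The extension has its own safeguards.** Section 10.4 sets withdrawal criteria for liver enzymes, QTc, suspected interaction and attributable serious events, and stops dosing in all subjects if a criterion is met in two or more. Entry requires benefit, good tolerability and separate consent, and safety visits are scheduled. These matter for patient protection, but they act once a signal appears and are not evidence for the duration.

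**Larger figures.** Two are tempting, and neither is supported.
- A reader might add the courses, 12 + 52 = 64 weeks, and compare that with a 13-week study. The sum is cumulative. Visit 7 falls 12 weeks after dosing stops, so the courses may be separated by a drug-free interval, and continuous exposure of 64 weeks is not established.
- A reader might take "up to 33 days extra YF476 may be taken by each patient" (Section 20.1) to mean that the initial course itself can pass 13 weeks. The 33 days is the sum of all visit windows: 2×2 + 3×3 + 4×5 = 33. It includes Visit 7, which falls after dosing has stopped. The windows are set around scheduled days, and Visit 6 is scheduled at 84 days, so the initial course ends by 84 + 3 = 87 days, below 13 × 7 = 91.

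**Conclusion.** The point holds as an internal contradiction on a safety limit the protocol states for itself. Stated support is 13 weeks and permitted extension dosing is up to 52 weeks, 4 times as long; it is 24 weeks if a patient stops at Visit 10. The risk and benefit-risk text in Section 7.9 has not been brought into line with the extension.

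The conclusion rests on the protocol alone. It assumes that a general reference to the Brochure does not override an explicit statement of duration. The 52 weeks is a maximum, and the comparison uses the extension by itself. A reader might also infer that the extension must be held back until the matter is settled. The documents do not support that step: they show two statements that disagree, not which one is right. That decision is clinical and toxicological.

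**What to change.** Reconcile Section 7.8.4 (toxicology), Section 7.8.5 (AUC margin) and Section 7.9 (dose regimen, endoscopy risk, benefit-risk) with Sections 2.6, 9, 11.1 and 14.8 to 14.12. Afterwards:
- the stated toxicology support, meaning study length, no-effect level and AUC margin, and the permitted dosing duration should agree;
- the endoscopy item should count the extension's procedures;
- the benefit-risk paragraph should address the extension explicitly and may refer to the Section 10.4 rules.

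Which side is corrected is for the sponsor. If longer data already exist, the cost is a few sentences and a citation. If they do not, the sponsor has a substantive decision to make, and this review takes no position on it. The inconsistency can be removed without touching the sample size, endpoints or analyses. Any substantial amendment needs the approvals set out in Section 20.1.
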